The research coordinator will obtain the providers' written informed consent for the study participation; a fully signed copy will be provided to the provider and another copy will be kept on file in a locked cabinet in [name] office at MetroHealth.

Following recruitment and informed consent procedures, OB providers will be randomized by practice into one of two study arms: (1) the intervention arm utilizing NEST or (2) the control arm utilizing standard practice patterns for education and counseling (usual care). Randomization by practice will prevent contamination between study arms, as a patient may see more than one provider within a practice over the course of her pregnancy. A cluster will be an outpatient clinic and contain the providers who practice at that location. The intervention will be delivered to the cluster as a whole. Thus, all participating providers within a cluster will be randomized to the same arm. Practices within the healthcare system will be stratified by both practice and patient-population characteristics. A binary random number generator will be used to assign NEST or control status at the practice level. The assignment will be checked to ensure a balance with respect to the number of clusters and providers in each of the study arms. Imbalances will be corrected manually, and the resultant groupings will be checked to ensure that randomization has been preserved. Participating providers in practices randomized to the intervention arm will receive a training session to orient them to NEST prior to data collection activities. Because NEST is targeted to affect the patient-provider interaction, study participants will not be blinded to which group they have been allocated.

All participating providers at Cleveland Clinic and MetroHealth will be asked to review the most current clinical practice guidelines as developed by the American College of Obstetricians and Gynecologists (ACOG) and Society for Maternal Fetal Medicine (SMFM). These guidelines will be emailed to each provider once their first patient has expressed interest in participating.

We will return to previous methods of enrolling providers into the NEST study at both MH and CCF.

DATA COLLECTION INSTRUMENTS AND PROCEDURES

We will utilize the same data collection instruments at both the Cleveland Clinic and at MetroHealth.

I. Pregnant participants

Data collection instruments and intervention:

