As a follow-up measurement, the Cleveland Clinic study team will conduct semi-structured interviews (Amendment #14). In doing so, we will gain further understanding of the decision-making process for prenatal genetic tests in addition to gain further information regarding the usability, feasibility and acceptability of the NEST intervention. Participants will include women who meet the criteria for the NEST study, and are either: in the 3rd trimester of pregnancy or have delivered in the last 12-months. This population reflects women who have completed the prenatal genetic test decision-making process and can provide key insight into ways to improve the best support that process. We will contact participants who meet inclusion criteria regarding participation in in-depth telephone interviews via MyChart or email, whichever has been the approved method (by the participant) for contact as part of the NEST study. Before re-contacting is initiated, a research team member will review to determine if individuals meet inclusion criteria. This will include a review of 1) the medical record of eligible participants to determine if any obstetrical complication has occurred that would constitute exclusion and 2) the research documentation to determine if an eligible participant withdrew or was withdrawn from the NEST study. These individuals will not be re-contacted.

3) Direct observation: We will use a method of direct observation (DO) to measure shared decision-making, the primary outcome of the study. We will measure this by audio-recording the visit and then using (1) the OPTION scale, a validated scale of shared decision-making and (2) a content checklist to assess the content and discussion of the visit. See Data analysis below for further description.

We will audio record patient-provider discussions during the first prenatal visit of those patients who provide written informed consent to do so. The research assistant will give the recorder to the patient to record the content, interaction, and duration of dialogue pertaining to genetic risk and risk assessment. We have elected to audio record instead of video record in an attempt to minimize the Hawthorne effect and because of the sensitive nature of the physical exam that takes place during this visit. Patients are given the option

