to either (1) record the whole appointment. If this happens the research assistant will only transcribe the dialogue pertaining to prenatal genetic screening, or, (2) to turn on the recorder when the discussion regarding prenatal genetic screening is taking place.

As recent guidelines have changes, we will again be offering patients the option to consent to audio-recording during their first visit for the CCF and MetroHealth sites.

4) QPV: This survey will be administered approximately 7-10 days following the first visit when the basic concepts associated with prenatal genetic testing have been introduced. It will be administered using online REDCap survey. Unless otherwise specified by the participant.

5) QTT: This survey will be administered between weeks 12-22 EGA once the participant has made a decision about if to undergo prenatal genetic testing (or at the EGA at which the opportunity has closed in the case of those participants who elect against testing). It will be administered using online using REDCap survey. Unless otherwise specified by the participant.

6) QFF: This survey will be administered between weeks 22-24 EGA. It will be administered using online using REDCap survey. Unless otherwise specified by the participant.

A review of the medical record will be conducted prior to communication about each survey to ensure that the participant continues to meet inclusion criteria. Individuals who experienced a complication or fetal demise as documented at the time point of QPV, QTT and QFF, or who no longer receive care at the Cleveland Clinic or MetroHealth, depending on original site of enrollment and will not be contacted to complete the survey(s). Each study site, either Cleveland Clinic or MetroHealth, will be responsible for all subsequent chart reviews and administration of all QPV, QTT and QFF surveys for all participants enrolled at those sites. All patients will receive a research stipend of the following amounts for each of the completed surveys from the Cleveland Clinic Accounts Payable Offices (patients will receive up to \$150.00):

- 1) QBASE - \$25.00
- 2) QPV - \$25.00
- 3) QTT - \$50.00
- 4) QFF - \$50.00

II. Partners of participating pregnant patients

We will utilize the same data collection instruments and procedures at both the Cleveland Clinic and MetroHealth.

Data collection instruments: This includes the QBASE and QPV, both identical to the questionnaires administered to pregnant participants.

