Data from the surveys will be collected either 1) using a tablet PC enabled with REDCap Survey for direct data entry or, if necessary, due to technical issues 2) on paper surveys with manual entry by the research team into REDCap. This is only done if there is a technical issue with the iPads or printers (internet connectivity problems, battery issues, etc.).

The following analysis will be conducted with the Principal Investigator in conjunction with [name], the QHS statistician designated to the WHI using JMP and SAS:

Data from the direct observation will be analyzed using the *observed* OPTIONS scale. This is a validated scale similar to the *dyadic* OPTIONS scale but developed for direct observation measurement of SDM in the clinical encounter. The *observed* OPTIONS scale will be utilized in conjunction with a content checklist to determine if the information exchanged during discussions of prenatal genetic risk and assessment meets the needs and preferences of patients, the recommendations of OB providers and GCs published by the American College of Obstetricians and Gynecologists, and clinical practice guidelines. The checklist was developed using data from our preliminary studies.

Audio recordings from the direct observation will be transcribed verbatim for analysis. Transcriptions will be coded by two independent coders using the *observed* OPTIONS scale and content checklist. Measures will be analyzed as a function of exposure (NEST vs. control) and visit composition (patient only vs. patient/partner pairs). The content checklist will be utilized to assess discussion content and to determine fidelity to the intervention. Transcriptions will be time-stamped to determine the length of discussions pertaining to prenatal genetic risk and assessment in NEST vs. control groups. Tukey-Kramer comparisons will be made to adjust for multiple comparisons. The matrix of predictor variables of intervention, patient characteristics, including variables of baseline knowledge and attitudes, presence of partner at the visit, and provider characteristics will be examined using the co-linearity tests of variance inflation factors and condition indices. Those variables exhibiting sufficient independence will be included in the multivariable analysis. Kappa statistics will be calculated to assess the degree of agreement between the coders; a third coder will be brought in if consensus cannot be reached.

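### No stated step masks the coders who rate the primary shared decision-making score, and no common rule fixes the segment they rate, so both can differ by arm

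*Combined protocol and SAP*

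**What the plan says.** **Outcome.** Under Data collection procedures, item 3 (Direct observation): "We will use a method of direct observation (DO) to measure shared decision-making, the primary outcome of the study". The visit is audio-recorded and scored with the OPTION scale and a content checklist.

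**Recording.** The same item says "The research assistant will give the recorder to the patient to record the content, interaction, and duration of dialogue". The patient then has two options. She may record the whole appointment, in which case "If this happens the research assistant will only transcribe the dialogue pertaining to prenatal genetic screening". Or she may choose "to turn on the recorder when the discussion regarding prenatal genetic screening is taking place".

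**Scoring.** Under Data Analysis, "Transcriptions will be coded by two independent coders", using both the observed OPTION scale and the checklist. The section adds: "The content checklist will be utilized to assess discussion content and to determine fidelity to the intervention". Kappa is calculated, and a third coder is brought in where consensus fails. A second comparison uses the same material: "Transcriptions will be time-stamped to determine the length of discussions pertaining to prenatal genetic risk and assessment in NEST vs. control groups".

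**Blinding.** The randomisation paragraph under OB providers says "study participants will not be blinded to which group they have been allocated". The plan does not say whether transcribers or coders are masked.

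**Editing.** Data Management (Audio-recordings) removes personal identifying information from audio and transcripts. It does not mention study arm, clinic or NEST.

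**The concern.** Patients and providers cannot be blinded in this trial, so the primary outcome can be protected from allocation bias only at recording, segment selection and rating. The plan sets no arm-related safeguard at any of the three.

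At rating, coders make a judgement about how far a conversation shared the decision. They read transcripts in which NEST patients and providers may well refer to the report in their hands, and they also complete the form that feeds the fidelity assessment. A coder who infers the arm may rate accordingly, without intending to.

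At recording, a woman holding a printed NEST report may recognise the start of the genetics discussion at a different moment from a control woman. The opening of that discussion is where priorities are set, which is what NEST is meant to change. A different starting point alters both the scored content and the measured length.

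At stake is whether a difference between arms on the primary outcome, or on discussion length, can be attributed to NEST and not to how it was measured.

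**Working it through.** The plan gives no figure to reproduce on this point. The first check sets each measurement step beside the safeguard stated for it.

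| Step | Who controls it | Safeguard stated | Does it deal with arm? |
|---|---|---|---|
| Recorder started for the genetics discussion only | Patient, not blinded | None | No |
| Segment chosen from a whole-visit recording | Research assistant | Limited to the topic; no start/stop rule, no masking | No |
| Transcript editing | Study staff | Personal identifiers removed | No |
| OPTION rating | Two coders | Validated scale, independent coding, kappa, third coder | Agreement only |
| Checklist, used for fidelity | The same two coders | No order of scoring stated | No |

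On the second row, the Study Intervention text has a research assistant print the NEST report and review it with the patient. The closing CCF Procedures list gives transcription to NEST study staff. The plan does not say that these are different people, or that whoever transcribes is unaware of the arm.

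**Why agreement statistics do not help.** Suppose both coders add the same amount d to every NEST transcript.

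- Coder 1 minus coder 2 on one transcript: (true + d) − (true + d) = 0, so no disagreement appears.
- NEST mean minus control mean: true difference + d.

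The coders agree fully, no third coder is called, and the arm difference is wrong by d.

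**Scale, on assumed values only.** The documents give no sample size, SD, intracluster correlation or number of clusters for the main trial. Assume no true effect, a two-sided 0.05 test, a measurement shift of b SD between arms, and n the effective number per arm after allowing for clustering. Then

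false-positive rate = Φ(b√(n/2) − 1.96) + Φ(−b√(n/2) − 1.96).

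For b = 0.2 and n = 50, b√(n/2) = 0.2 × 5 = 1.00, so the rate is Φ(−0.96) + Φ(−2.96) = 0.1685 + 0.0015 = 0.170.

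| Shift b | n = 30 | n = 50 | n = 100 | n = 150 |
|---|---|---|---|---|
| 0.1 SD | 6.7% | 7.9% | 10.9% | 13.9% |
| 0.2 SD | 12.1% | 17.0% | 29.3% | 41.0% |
| 0.3 SD | 21.3% | 32.3% | 56.4% | 73.8% |

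The rate rises with n, so recruiting more women does not cure a shift of this kind. The table shows what a shift would do if it occurred. It is not evidence that one occurs.

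**The case against.** **The checklist is a general form.** Data Analysis describes it as covering patient needs, professional recommendations and practice guidelines, and it is applied in both arms. A reader might infer that completing it tells the coder the arm. The documents do not support that: the same form is filled in for every transcript, and the plan does not say who turns it into a fidelity judgement. What stands is that the plan is silent on masking and that the dialogue itself is likely to mention the NEST report.

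**Control women are alerted too.** Those who agree to audio know that the genetics discussion is to be recorded, and they complete QBASE beforehand. This narrows the contrast, but NEST women alone carry a report on the topic.

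**Visits without a discussion.** A reader might infer that control visits with no genetics discussion go unrecorded and raise the control mean. If a share f of control visits would score 0 and the rest average 30 on a 0–100 scale, losing them adds 30 − 30(1 − f) = 30f. That is 1.5, 4.5 or 7.5 points for f = 0.05, 0.15 or 0.25. Every input is assumed. The result is an upper bound on the bias in the arm difference, because it needs every such visit to use the patient-started option and no NEST visit to lack a discussion. The recruitment section also treats discussion of prenatal testing at the first visit as standard practice, and the QPV timing presumes that the topic was introduced. These points are not an estimate of bias here.

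**Compulsory whole-visit recording.** It might seem the obvious remedy. But audio is optional, the consent process describes recording the genetics discussion, and the plan itself notes the sensitivity of the examination. More refusals would shrink the primary-outcome sample and add selection. This objection stands.

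**Existing safeguards.** A validated scale, two coders and a third for disputes are sound practice. They protect reliability, not freedom from a shared bias.

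**Conclusion.** The concern holds in a limited form. The plan has no step that masks the raters of a judgement-based primary outcome, and no rule that makes the scored segment comparable between arms. Ratings, scored content and discussion length can each differ by arm for reasons of measurement. Masking is not mentioned, which is not the same as saying that coders know the allocation; that they may infer it is a reasonable expectation, not a documented fact.

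The net direction is unknown. Favourable rating of recognised NEST transcripts would exaggerate a benefit, while loss of poor control visits would hide one. The size cannot be derived from the documents, and the false-positive rates above rest wholly on the assumed shifts and effective sample sizes. The change is worth making because the rating safeguards are cheap and concern the primary outcome.

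**What to change.** **Rating.**

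- In the edit that already removes identifiers, replace references to NEST, clinic and arm with a neutral placeholder. Keep the surrounding dialogue, so that the exchange OPTION is meant to score is not lost.
- Give transcripts to the coders in random order without arm labels.
- Lock both coders' OPTION scores before the fidelity checklist is opened.

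These steps can apply to any recording not yet scored.

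**Recording.**

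- Keep both options, but present whole-visit recording as the preferred default.
- Log the mode used.
- Apply one written rule for where the scored segment starts and stops, whichever mode was used.
- Record when a visit with audio consent produced no recording or contained no genetics discussion, and state in advance how each is handled.
- Report the shared decision-making and duration comparisons by recording mode as a sensitivity analysis. Mode is chosen by patients after allocation, so these results describe robustness and are not randomised subgroup comparisons.

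**Cost.** A short protocol amendment, slightly more editing, and a check that the consent wording fits whole-visit recording as the default. No extra staff are needed. Masking will remain incomplete for some transcripts, where the conversation itself gives the arm away.

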The delivery of high-quality, evidence-based prenatal care and access to NIPT will only occur if patients have information and support to make informed, values-based choices about their prenatal testing options. Given that informed decision-making is positively correlated with higher healthcare quality, it is critical to have effective, evidence-based mechanisms that are responsive to the needs and priorities of patients, the day-to-day challenges faced by providers, and the current scientific evidence and clinical practice guidelines about NIPT. While it is recognized that providers should involve patients in healthcare by means of a SDM process, how to achieve that level of communication within the constraints and challenges of the practice of obstetrics remains unknown. Thus, the **goal** of this study is to conduct a cluster, randomized trial to test an evidence-based tool termed NEST (for NIPT Education Support Tool) to support patients' decision-making, focusing on the communication that takes place in the clinical encounter. We will also identify aspects of the patient-provider interaction that are key to implementing effective strategies responsive to the challenges posed by the continued development of NIPT. Our hypothesis is that, by focusing on the dynamic interaction between the patient and provider, NEST will result in a SDM process that, in turn, will both increase patients' ability to make an informed choice about NIPT and decrease the decisional conflict associated with that choice. The expected outcome of this study is a clinically relevant, point-of-care tool that can be utilized among a diverse group of patients and providers to facilitate decisions that are informed, consistent with the patient's values, and with which patients do not experience decisional conflict. This study is significant because the findings and end products will help expectant parents to have informed access to the most recent advance in prenatal genetic science. This project is also relevant to translational research, as informed decision-making is a crucial step in bringing new genetic technologies from the bench to the bedside. We anticipate that this study's findings will ultimately contribute to improving the quality of prenatal care by empowering pregnant women to make informed choices that reflect their needs and preferences as individuals and parents. We also anticipate that OB providers will feel more prepared and confident when approaching conversations about NIPT.

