1) QBASE: Once informed consent has been obtained, all participants will complete the QBASE. This will be administered on a CCF-compliant tablet and using REDCap survey. The research team member does come with a paper copy of the QBASE as a backup for any technical difficulties. If the paper survey is used, it would be manual entered by the research team into REDCap.

2) NEST Intervention: Participants scheduled to see an OB provider randomized to the NEST (randomization occurs at the level of the OB provider) will be asked to complete the NEST. This will be administered on a CCF-compliant tablet and using REDCap survey. After completion, patient participant will be given two printed copies of the NEST, one for the patient and one for their provider, to review during their office visit. The participating provider will be given a copy of the NEST to help tailor the conversation to the patient's needs. Patients who are scheduled to see a provider at a practice randomized to the control arm will receive standard care.

As recent guidelines have changes, we will again be enrolling patients from designated intervention branches for the CCF and MetroHealth sites.

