For those patients/partners and providers who both opt-in to direct observations, the audio will be summed in accordance with the OPTIONS scale instructions, and the results for patients/partners and providers will first be analyzed separately as a function of intervention (NEST vs. control). The data from patients/partners and providers will be combined in a data set matching patient and provider responses. The difference between matched pairs will be computed for SDM broadly, and components of SDM as described by OPTIONS will be computed individually, sorted by type of intervention, and, with the t-test, checked to see whether, within study arms, the means of the differences are significantly different from zero.

DATA MANAGEMENT

All study information will be maintained in a secure fashion as delineated by the Cleveland Clinic IRB, either in a locked cabinet in the WHI or on a secure, encrypted research computer. We will use IRB-approved level of encryption on the computer. Only research personnel will have access to these files. In addition, all personal identifying information recorded per IRB and informed consent purposes will be kept in a separate location from data to be used for analysis purposes.

Confidentiality of patient information will be maintained at all times. The study will have Institutional Review Board approval prior to recruitment of any patients at participating clinical sites. All study investigators and research team members will document completion of Human Subjects Protection Training prior to initiating any study procedures. This requirement may be met by completing the NIH course, the CITI (Collaborative Institutional Training Initiative) program, or another course as required by the member institution.

Cleveland Clinic:

Masterlist: A master list will be maintained that will allow researchers to link participants with their ID numbers only for the following purposes:

- 1) Documentation and distribution of gift card/ research stipend in appreciation of subject's time and participation in the study.
- 2) To link pregnant participants' and clinicians' responses during the data analysis phase as needed. Any linkage will be de-identified after data analysis is complete.
- 3) To investigate any adverse events: A data safety and monitoring protocol has been put into place. If any adverse events are identified, then the master list will be used to link the participant with her personal identifying information for this purpose.

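### The trial randomises outpatient practices, but the analysis of the direct-observation outcomes, including the primary outcome, specifies no method that accounts for clustering

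*Combined protocol and SAP*

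**What the plan says.** Background and Significance states that the goal "is to conduct a cluster, randomized trial to test an evidence-based tool termed NEST". The randomisation text under III. OB providers says "OB providers will be randomized by practice into one of two study arms" and defines the unit: "A cluster will be an outpatient clinic and contain the providers who practice at that location". On allocation it adds: "Practices within the healthcare system will be stratified by both practice and patient-population characteristics". It also says: "The assignment will be checked to ensure a balance with respect to the number of clusters and providers in each of the study arms". Any imbalance found is then put right by hand.

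In the pregnant participants' Data collection procedures, item 2 (NEST Intervention) has a parenthesis reading "randomization occurs at the level of the OB provider". The same item later speaks of a practice being randomised to control.

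The primary outcome is shared decision-making, scored from an audio recording of the first prenatal visit (item 3, Direct observation). For these data the Data Analysis section says "Measures will be analyzed as a function of exposure (NEST vs. control) and visit composition (patient only vs. patient/partner pairs". It then names:

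- Tukey-Kramer comparisons;
- a predictor list of intervention, patient characteristics, partner presence and provider characteristics, screened for collinearity;
- a multivariable analysis whose model is not stated;
- kappa for coder agreement.

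Matched patient-provider differences are to be sorted by intervention and, "with the t-test, checked to see whether, within study arms, the means of the differences are significantly different from zero".

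Neither this section nor any other mentions a random effect, GEE, cluster-robust variance, cluster-level analysis, ICC or design effect. The documents also give no significance level, number of practices, visits per practice or sample size for the trial. The only target, 40 participants, belongs to the interview sub-study.

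**The concern.** NEST is assigned to whole practices, so differences between practices that have nothing to do with NEST enter the treatment contrast directly. Women at one clinic share providers, training and local habits, and one provider can contribute many recorded visits. An observed shared decision-making score largely reflects how the provider conducts the conversation, so some correlation within practice and within provider is to be expected.

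An analysis at encounter level with no term for this counts correlated visits as separate pieces of evidence. Standard errors are then too small, confidence intervals too narrow and p-values too low, on the primary outcome. The silence also leaves the analyst free to choose the unit of inference after seeing the data.

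**Working it through.** **Step 1: compare design with analysis.** The design text fixes the practice as the unit of allocation. The analysis text lists its predictors, and neither practice nor provider identity is among them. Provider characteristics are listed, but as fixed covariates they explain only the part of between-provider variation that they measure. The phrase about variables being sufficiently independent concerns collinearity among predictors, not independence of observations.

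**Step 2: inputs.** The plan has no figure to reproduce. Everything numerical here is an assumption: two-sided alpha 0.05, recorded visits per practice m from 5 to 40, ICC from 0 to 0.20.

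**Step 3: formulas.**

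- Design effect: DE = 1 + (m − 1) × ICC
- Naive SE ÷ true SE = 1/√DE
- Actual type I error = 2 × [1 − Φ(1.96/√DE)]

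Example with m = 20 and ICC = 0.05: DE = 1 + 19 × 0.05 = 1.95; √1.95 = 1.396; 1.96/1.396 = 1.404; type I error = 2 × [1 − Φ(1.404)] ≈ 0.16.

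| m | ICC | DE | Naive SE ÷ true SE | Actual type I error |
|---|---|---|---|---|
| 5 | 0 | 1.00 | 1.00 | 0.050 |
| 5 | 0.01 | 1.04 | 0.98 | 0.055 |
| 5 | 0.05 | 1.20 | 0.91 | 0.074 |
| 10 | 0.05 | 1.45 | 0.83 | 0.104 |
| 20 | 0.05 | 1.95 | 0.72 | 0.161 |
| 20 | 0.10 | 2.90 | 0.59 | 0.250 |
| 40 | 0.10 | 4.90 | 0.45 | 0.376 |
| 40 | 0.20 | 8.80 | 0.34 | 0.509 |

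**Step 4: simulation.** There were 10,000 null trials per setting, with 4, 6 or 10 practices per arm, m = 10 or 20, equal cluster sizes, and ICC 0, 0.01, 0.05 or 0.10. An ordinary two-arm t-test on encounters stands in for an analysis with no cluster term; the plan does not itself name a two-arm t-test. With 6 practices per arm and m = 20 it rejected in 7.0%, 16.2% and 25.0% of trials at ICC 0.01, 0.05 and 0.10, in line with the formula. The number of practices made little difference to this inflation. A t-test on practice means rejected in 4.5% to 5.7% of trials across all settings.

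**Step 5: the within-arm t-test.** A one-sample t-test within one arm, in the same setting (6 practices, m = 20), rejected in 6.9%, 16.5% and 24.6% of trials. The inflation is the same, but this test asks whether patient and provider scores differ within an arm. It does not compare NEST with control.

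**The case against.** The strongest reply is that the plan is silent rather than wrong. A reader might infer that every named analysis treats encounters as independent and that the false-positive rate therefore exceeds 5%. The documents do not support that. The sentence on exposure and visit composition names no method, the multivariable model is unspecified, and Tukey-Kramer adjustment can be applied within a mixed model. Kappa and the collinearity checks do not test the intervention. With ICC 0 there is no inflation, and recording is optional, so visits per practice may be few. At m = 5 and ICC 0.01 the excess is about half a percentage point.

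Other stronger readings also fail:

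- The only named t-test is within arm, so it cannot show that NEST versus control intervals are too narrow.
- No inferential method is named for the informed-choice or decisional-regret surveys, so the fault there is omission rather than a wrong method. No binary informed-choice endpoint is defined.
- The provider-level parenthesis does not prove that the analyst would use the wrong unit, since the same item refers to a randomised practice. Visits are clustered under either reading.
- It goes too far to say that a positive result could not be defended. The master list allows patients to be linked to clinicians for analysis, so a valid analysis appears possible with the same data.

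These points narrow the claim but do not remove it. An analyst could follow the text exactly, fit a model with no cluster term and be fully compliant. For a primary outcome driven by provider behaviour, an ICC of exactly zero is implausible.

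**Conclusion.** The concern holds in conditional form. The plan randomises practices and specifies nothing, for the primary or other direct-observation outcomes, that accounts for clustering. Followed as written, it understates the NEST versus control standard error for any positive ICC with more than one visit per practice. Over plausible assumed values the type I error runs from about 5.5% (m = 5, ICC 0.01) through 10% and 16% to 25% (m = 20, ICC 0.10), and higher for larger clusters. These figures rest on assumed m, ICC and alpha and on equal cluster sizes; the documents cannot narrow the range. The point should be settled before analysis because it decides the error bars on the primary comparison. Power under a correct analysis cannot be computed, since the documents give no cluster count, effect size or standard deviation.

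**What to change.** In the Data Analysis section:

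1. Name one cluster-aware primary model. For example, use a linear mixed model for the observed shared decision-making score, with NEST and the stratification factors as fixed effects, a random intercept for practice (and for provider within practice if estimable), and small-sample degrees of freedom such as Kenward-Roger. List the stratification factors, which are now described only in general terms. Run any Tukey-Kramer comparisons within this model.
2. Specify a t-test on practice means as a supporting analysis, or as the fallback if there are few practices.
3. Apply the same principle to the within-arm matched-difference test and to the survey outcomes, naming a method for each survey outcome.
4. State alpha and the number and size of clusters, and report the ICC.
5. Reconcile the parenthesis in the NEST Intervention item with the randomisation text, so that the practice is the unit throughout.
6. Use a permutation test only if it reproduces the actual allocation procedure, including the manual corrections; an unrestricted reshuffle of practices would not.

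This needs no new data collection, provided that practice and provider identifiers are carried into the analysis data set. SAS, already named, can fit these models. The cost is wider but correct intervals. Degrees of freedom may be few: with 4 practices per arm, the t-test on practice means has 2 × 4 − 2 = 6.
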